10.9.5. Response Review

N/A

11. REGULATORY CONSIDERATIONS

11.1. Institutional Review of Protocol

The protocol, the proposed informed consent and all forms of participant information related to the study (e.g. advertisements used to recruit participants) will be reviewed and approved by the Stanford IRB and Stanford Cancer Institute Scientific Review Committee (SRC). Any changes made to the protocol will be submitted as a modification and will be approved by the IRB prior to implementation. The Protocol Director will disseminate the protocol amendment information to all participating investigators.

11.2. Data and Safety Monitoring Plan

The Stanford Cancer Institute Data and Safety Monitoring Committee (DSMC) will be the monitoring entity for this study. The DSMC will audit study-related activities to determine whether the study has been conducted in accordance with the protocol, local standard operating procedures, FDA regulations, and Good Clinical Practice (GCP). This may include review of the following types of documents participating in the study: regulatory binders, case report forms, eligibility checklists, and source documents. In addition, the DSMC will regularly review serious adverse events and protocol deviations associated with the research to ensure the protection of human subjects. Results of the DSMC audit will be communicated to the IRB and the appropriate regulatory authorities at the time of continuing review, or in an expedited fashion, as needed.

11.3. Data Management Plan

The Protocol Director, or his designee, will prepare and maintain adequate and accurate participant case histories with observations and data pertinent to the study. Study specific Case Report Forms (CRFs) will document treatment outcomes for data analysis. Case report forms will

be developed using the REDCap database system and will be maintained by the Study Coordinator. CRFs will be kept in a locked office, only accessible to the research team.

12. STATISTICAL CONSIDERATIONS

12.1 Statistical Design

The purpose of this clinical study is to determine the initial safety and utility of BioAesthetics' NACgraft™. The proposed sample size of 15 subjects is not intended to support definitive conclusions around our primary outcome measures, but rather to:

- Provide support that the NAC graft is safe for marketing purposes
- Confirm ability to gather necessary data for an adequately powered larger clinical study in the future
- Provide preliminary estimates of these measures and their associated variability, in part to better define sample size requirements for a future larger study.

Outcome measures for this study address:

- Safety: For safety, we are collecting data on the degree of healing and the incidence of engraftment- related adverse events (e.g. infection, necrosis).
- Performance: For graft performance, we are collecting data on the following:
 - Degree and timing of healing
 - Duration of surgical engraftment procedure
 - Nipple characteristics
 - Projection
 - Sensitivity
 - Vascularization
- Patient Satisfaction: Finally, we will access user experience from satisfaction surveys addressing the following areas:
 - Body image
 - Overall satisfaction
 - Satisfaction with nipple
 - Self-esteem
 - Psychological well-being

Additionally, we will assess the completeness of feasibility study data in terms of missing or incomplete measurements for each outcome and will determine any associated operational modifications needed to enhance data collection in a future study. Preliminary estimates will be developed for each type of measure. Each estimate will be assessed with descriptive statistics (t distribution for continuous variables, Poisson distribution for incidence rates, etc.) and 95% confidence intervals will be applied.

12.1.1. Randomization

No randomization will take place.

12.2. Interim analyses

No statistical stopping rule will be employed.

12.3. Descriptive Statistics and Exploratory Data Analysis

Descriptive statistics will be employed including t distribution for continuous variables, Poisson distribution for incidence rates, etc. and 95% confidence intervals will be applied for the measured primary and secondary outcomes.

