2.4. Study Design

This **single arm** pilot study is designed to obtain preliminary safety and performance data in adult female subjects following **treatment** with the BioAesthetics' NACgraft™. NACgrafts will be surgically engrafted onto 15 patients, via uni- or bilateral onlay engraftment. Given the nature of the treatment, this is an **open** (no masking) trial. **No randomization** will occur. The primary outcome being evaluated is **safety/efficacy** of the treatment approach. The overall study design is as follows:

- Potential patients will be screened to determine study eligibility up to 3 weeks before the engraftment.
- On the day of surgery, NACgrafts will be engrafted according to standard reconstructive technique. Using sterile technique, the recipient site on the breast mound will be de-epithelialized sharply and meticulous hemostasis obtained with electrocautery. The NACgraft™ will then be sutured into the wound bed with dissolving suture. In women undergoing bilateral NAC reconstruction, this process will be repeated for the contralateral breast. A sterile dressing will be applied and patients will be discharged home according to institutional guidelines; written instructions will be provided for the care of the NACgraft(s) and dressings. The dressing will include antimicrobial ointment, followed by a non-adherent, occlusive dressing (e.g. Adaptic, Xeroform) secured in place using a foam dressing cut into a donut (e.g., Allevyn) to prevent compression of the graft.
- Safety, healing time, sensation, vascularization, patient satisfaction, and nipple characteristics will be assessed over a 12-month period. Patients will return to the outpatient clinic on postoperative Days 7, 14, 28, and 42. Visits thereafter will take place on days 90, 180, and 360 post-engraftment.

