10.1.2. Measurement Definition

Time to healing for each NACgraft will be as the first weekly visit at which the surgeon deems the graft >99% overall healed. This measurement will be reported as the number of weeks to healing.

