10.3.2. Measurement Definition

Time to 50% and 75% healing for each NACgraft™ will be as the first weekly visit at which the surgeon deems the graft >50% healed and >75% healed, respectively. This measurement will be reported as the number of weeks to healing.

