10.4.3. Measurement Methods

Operative time will be measured in the procedure room with a standard stopwatch and reported in minutes/seconds. If in the operating room this is reported by operating staff. If done in the clinic, the procedural nurse will assist with timekeeping. Operative time will be recorded separately for each NACgraft™ during bilateral procedures.

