12.4.2. Analysis Plan

Time to complete healing for each NAC will be defined (as described in **Section 10.1**) as the first weekly visit at which the surgeon deems the graft >99% overall healed. This outcome will be characterized in terms of distributional characteristics such as the maximum, mean, median, and variation (as 95% confidence interval) of these data.

Safety outcome data as described in **Section 10.2** that are reported as percentages (ischemia/necrosis, erythema, dehiscence) will be characterized in terms of distributional characteristics such as the maximum, mean, median, and variation (as 95% confidence interval). Measurements reported as categorical variables (infection) will be characterized as a percent.

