12.5.2. Analysis Plan

Secondary outcome data as described in **Section 10.3 – 10.9** will be characterized in terms of distributional characteristics such as the maximum, mean, median, and variation (as 95% confidence interval). Numerical scores (weeks to 50% and 75% graft healing, operative time, nipple projection, nipple diameter, NAC sensitivity, weeks to NAC vascularization, and LIKERT survey scores) will be characterized in terms of distributional characteristics such as the maximum, mean, median, and variation (as 95% confidence interval). Measurements reported as categorical variables (infection) will be characterized

as a percent.

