Answer the following items as compared to before your breast reconstruction(s).	Much Worse	Worse	About the same	Better	Much Better
My sense of body image is					
My sense of self-esteem is					
My sense of well-being is					
My sex life is					
	Strongly Disagree	Disagree	Neither Agree nor Disagree	Agree	Strongly Agree
Before my mastectomy, my nipples were the same size.					
Before my mastectomy, my nipples were the same color.					
Before my mastectomy, my nipples were symmetrical.					
Nipple reconstruction will complete my breast reconstruction.					
Nipple reconstruction will improve my body image.					
Nipple reconstruction will improve my sense of self-esteem.					
Nipple reconstruction will improve my sense of well-being.					
Nipple reconstruction will improve my sex life.					

Nipple Reconstruction Satisfaction Survey – Post-operative

You have undergone nipple reconstruction with the BioAesthetics NACgraft. The following questions are designed to determine how satisfied you are with the outcome. By checking ONE box in each row below, please indicate how satisfied with your nipple reconstruction operation today. Thank you for your feedback.

Postop Visit: 3 month 6 month 12 month Other _____

	< 18	19 – 35	36 – 50	51 – 65	> 66
What is your present age?					

If you had bilateral nipple reconstruction, please answer the following questions for ONE side only. Then answer the same questions on the following page for the OTHER side.

Breast:  Right  Left	Strongly Disagree	Disagree	Neither Agree nor Disagree	Agree	Strongly Agree
I am pleased to have had nipple reconstruction.					
I am pleased with the position of my reconstructed nipple.					
I am pleased with the overall appearance of my reconstructed nipple.					
I am pleased with the symmetry of my reconstructed nipple.					
I am pleased with the color of my reconstructed nipple.					
I am pleased with the softness of my reconstructed nipple.					
I am pleased with the appearance of my reconstructed nipple when nude.					
I am pleased with the appearance of my reconstructed nipple when clothed.					
I am pleased with the size of my reconstructed nipple.					
I am pleased with the projection (sticking out) of my reconstructed nipple.					
My reconstructed nipple made my new breast look better.					
	No Sensation	Low	Normal	High	
What level of pleasant sensation do you have in your reconstructed nipple?					

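### Graft-level 95% intervals make no allowance for two grafts in one woman, and the infection percentage and the >95% healing rule name no denominator (minor)

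*Combined protocol and SAP*

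**What the plan says.** Section 2.4 sets the design: "NACgrafts will be surgically engrafted onto 15 patients, via uni- or bilateral onlay engraftment". The number of grafts can therefore lie anywhere from 15 to 30. The expected number of bilateral cases is not given.

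Several outcomes are defined on the graft:

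- Primary healing outcome, section 10.1.2: "Time to healing for each NACgraft will be as the first weekly visit at which the surgeon deems the graft >99% overall healed". Section 12.4.2 repeats the definition per NAC and asks for the maximum, mean, median and 95% interval of those values.
- Intermediate healing, section 10.3.2: "Time to 50% and 75% healing for each NACgraft™ will be as the first weekly visit".
- Operative time, section 10.4.3: "Operative time will be recorded separately for each NACgraft™ during bilateral procedures".
- Post-operative survey, Appendix B: "If you had bilateral nipple reconstruction, please answer the following questions for ONE side only". The same items follow for the other side. Section 12.5.2 ends its list of numerical scores with the survey: "LIKERT survey scores) will be characterized in terms of distributional characteristics such as the maximum, mean, median, and variation (as 95% confidence interval".

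The interval method comes from section 12.3: "Descriptive statistics will be employed including t distribution for continuous variables, Poisson distribution for incidence rates, etc. and 95% confidence intervals will be applied". Section 12.1 says the same. Neither section, nor anything else in sections 10 and 12, mentions a woman-level summary, a cluster adjustment or within-woman correlation.

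Other wording points to the woman. The relevant subset for each outcome (10.1.1, 10.2.1 and onward) is all 15 patients, and the analysis population in 12.4.1 and 12.5.1 is all participants.

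For complications, section 10.2.3 has the surgeon classify each graft for infection, and section 12.4.2 says: "Measurements reported as categorical variables (infection) will be characterized as a percent". Section 12.7 makes a healing rate above 95% one of its conditions for a positive study. Neither section names a denominator.

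**The concern.** Two grafts on one woman share her healing capacity, her surgeon and her aftercare, so their outcomes are likely to be correlated. A t interval over all grafts counts the second graft of a pair as a full new observation. The interval for a primary outcome then looks more precise than it is. Section 12.6.2 wants this pilot's estimates of variability in order to size a larger study, so false precision could be carried forward.

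The denominator is a separate matter and needs no assumption about correlation. If the unit is not fixed in advance, the same data can meet or miss the healing threshold in 12.7 according to a choice made after the results are known.

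**Working it through.** **Inputs.** From the documents: 15 women (2.4), hence n = 15 + b grafts with b bilateral women; a 95% t interval (12.1, 12.3); a threshold above 95% (12.7). The plan gives no interval width, precision target or power figure to reproduce. Not in the documents, so assumed: b from 0 to 15, and within-woman correlation ρ from 0 to 0.9. As a rough guide to b, the other-device series in 12.6.3 had 82 reconstructions in 50 patients. If each patient had one or two, 32/50 = 64% were bilateral, or about 10 of 15. That is illustrative only.

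**Step 1: design effect.** The variance of the graft mean is inflated by (n + 2bρ)/n.

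- b = 10, ρ = 0.5: (25 + 2×10×0.5)/25 = 1.40, so 25 grafts carry the information of 25/1.40 = 17.9. The pooled half-width is t(0.975, 24)/√25 = 0.413 SD. Allowing for pairing with 14 df it is t(0.975, 14)×√(1.40/25) = 0.508 SD.
- b = 15, ρ = 0.5: (30 + 15)/30 = 1.50, effective number 20.0, half-widths 0.373 and 0.480 SD.

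**Step 2: coverage of the pooled nominal 95% interval** (200,000 simulated trials per setting, normal data with a random patient effect):

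| Bilateral of 15 | Grafts | ρ = 0.2 | 0.5 | 0.7 | 0.9 |
|---|---|---|---|---|---|
| 3 | 18 | 94.3% | 93.1% | 92.3% | 91.3% |
| 5 | 20 | 93.9% | 92.1% | 90.7% | 89.4% |
| 10 | 25 | 93.1% | 90.1% | 88.1% | 85.8% |
| 15 | 30 | 92.5% | 88.8% | 86.2% | 83.5% |

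With b = 0 or ρ = 0 coverage is 95%. A t interval on the 15 woman means holds 94.9% to 95.1% throughout.

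Healing time can take only visit values, so a second check used weeks 1, 2, 4 and 6 with four assumed distributions and every graft healed by week 6, which is optimistic. With 10 bilateral women, pooled coverage ran from 92.9–93.2% at ρ = 0.2 to 86.6–86.8% at ρ = 0.9, against 94.6–94.9% for woman means. The conclusion does not depend on normality.

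**Step 3: the healing rule.** Count a woman as healed only if all her grafts are.

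- Over women, one unhealed graft gives 14/15 = 93.3%: fail.
- Over 20 grafts, 19/20 = 95.0%, which is not above 95%: fail.
- Over 21 grafts, 20/21 = 95.2%: pass. Over 25, 24/25 = 96.0%: pass.
- Two unhealed grafts fail even over 30 (28/30 = 93.3%).

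The two denominators therefore disagree exactly when one graft fails and b is 6 or more. With b = 6 and independent grafts at a healing probability of 95%, that chance is 21×0.05×0.95^20 = 0.38. Simulation over healing probabilities of 95–98% and ρ from 0 to 0.9 gives disagreement in 20–38% of trials with 6 bilateral women, 19–37% with 10, and none with 5 or fewer.

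**Step 4: complications with zero events.** The exact (Clopper-Pearson) upper 95% limit is 21.8% for 15 women, 13.7% for 25 grafts and 11.6% for 30 grafts if grafts are treated as independent. Allowing for latent correlation of 0.2–0.9, the graft-level limit is 14.2–18.6% for 25 grafts and 12.1–17.2% for 30. Part of the remaining gap is legitimate, because risk per woman and risk per graft are different quantities.

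**The case against.** **Silence is not a declaration of independence.** A reader might infer that the plan commits to treating grafts as independent. It does not say so, and a t interval on 15 woman means would also satisfy 12.3. The repeated subset of 15 patients can be cited for that reading. But those lines say who is included, not how two values from one woman become one, and 12.4.2 takes the interval from per-NAC values. Pooling remains the plain reading, and undercoverage is conditional on it. For the side-specific survey items the text points less clearly to pooling, so they are affected only if the two sides are in fact pooled.

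**The intervals drive no decision.** This stands. Section 12.7 uses no confidence interval, there is no statistical stopping rule, and 12.6.2 disclaims definitive conclusions. The per-graft data would also allow a correct interval later. With 3 to 5 bilateral women and ρ of 0.2 to 0.5, coverage is still 92.1% to 94.3%.

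**Infection is not a complete blank.** Section 10.2.3 classifies it by graft. Against the patient subset in 10.2.1, that leaves an ambiguity to reconcile.

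**The go-forward verdict.** A reader might take the 19–38% as the chance that the study's verdict reverses. The documents do not support that. Section 12.7 also requires no serious adverse events and adequate survey scores, so these figures only bound how often the overall verdict changes. They also assume healing near the threshold. With 10 bilateral women, disagreement is 12–20% at 99% healing, 7–11% at 99.5%, 18–21% at 90% and 8–10% at 85%.

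**Poisson.** A reader might also fault Poisson limits for yes/no endpoints. The open-ended wording of 12.3 leaves room for a binomial interval, 10.2.2 asks for event frequency as well, and the Poisson limit errs on the conservative side. It is not part of this point.

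**Conclusion.** The point holds in a limited form. The plan defines graft-level times, names a plain t interval and gives no rule for bilateral women. If grafts are pooled, the interval is too narrow by an amount that depends on two quantities the documents do not give. The shortfall in coverage is 1 to 4 percentage points with 3 bilateral women and up to 9 with 10, over the assumed correlations. It vanishes if there is no bilateral surgery or no correlation.

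The missing denominator is certain from the text. Whether it matters depends on having 6 or more bilateral women and exactly one unhealed graft, given that a woman counts as healed only when all her grafts are. It touches the healing component of 12.7, not the whole criterion. Severity is minor because the study is descriptive. The denominator is the part most worth settling beforehand, since it belongs to a decision rule.

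**What to change.** In 12.3, 12.4.2 and 12.5.2, state that 95% intervals for graft-level continuous outcomes and side-specific survey items take the woman as the independent unit. Use either a t interval on the 15 within-woman means or, if the graft is to stay the unit of description, a cluster-robust interval with 14 df. Means weight each woman equally; the second option weights each graft equally. Either way, add a rule for how a graft that never reaches >99% healed, or that is re-grafted under section 4, enters the analysis, because averaging does not settle that.

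Report complications and healing twice: per woman, with a Clopper-Pearson interval over 15, and per graft, with a cluster-adjusted interval. With zero events a variance-based adjustment collapses, so the per-graft limit should then use a correlation fixed in advance, as in step 4. Report the number of bilateral women and, where estimable, the within-woman correlation for planning.

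In 12.7, name before results are seen which denominator the rule uses. That choice is the sponsor's, since the graft is a defensible unit for a device pilot. Over women, with all grafts required to heal, the rule means 15 of 15. At 97% healing per graft, 10 bilateral women and ρ of 0 to 0.9, it is met in 47–56% of trials over women and 79–83% over grafts.

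The cost is wording, trivial analysis effort and somewhat wider intervals. With 10 bilateral women the pooled interval is 13–25% narrower than the woman-level one at ρ of 0.2 to 0.9. It is 8% narrower at ρ = 0, where the extra width buys nothing.

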12.4. Primary Analysis

Primary outcome measure: To evaluate safety and healing rates following NAC reconstruction using the BioAesthetics NACgraft™.

12.4.1. Analysis Population

All study participants will be included in the analysis population. Intention-to-treat analysis will be performed and statistics for sub-groups containing no missing data or non-adherence will be included.

12.4.2. Analysis Plan

Time to complete healing for each NAC will be defined (as described in **Section 10.1**) as the first weekly visit at which the surgeon deems the graft >99% overall healed. This outcome will be characterized in terms of distributional characteristics such as the maximum, mean, median, and variation (as 95% confidence interval) of these data.

Safety outcome data as described in **Section 10.2** that are reported as percentages (ischemia/necrosis, erythema, dehiscence) will be characterized in terms of distributional characteristics such as the maximum, mean, median, and variation (as 95% confidence interval). Measurements reported as categorical variables (infection) will be characterized as a percent.

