10.2.3. Measurement Methods

Photographs will be taken using standardized digital photography, stored and transmitted securely to surgeon for independent review. Grafts will be evaluated by the surgeon with the following metrics on a visual analog scale (VAS): ischemia/necrosis (0-100%); dehiscence (0-100%). In evaluating for complications, the surgeon will classify grafts as having A) no infection; B) hyperemia (no infection); C) cellulitis (superficial infection); D) abscess or purulent infection. Additional adverse events or complications (as defined in CTCAE v4.03, see **Section 7.2**) will also be recorded and reported in categorical format.

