12.6.2. Sample size justification

The proposed sample size of 15 patients is not intended to support definitive conclusions around our primary outcome measures, but rather will (a) provide support that the NAC graft is safe for marketing purposes, (b) will confirm our ability to gather the necessary data in an adequately powered larger clinical study in the future, and (c) provide preliminary estimates of the study measures and their associated variability, in part to better define sample size requirements for the larger study.

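### The t-based 95% CI that Section 12.4.2 puts on mean percent necrosis, erythema and dehiscence is uninformative when few grafts are affected; report patient incidence with an exact interval instead

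*Combined protocol and SAP*

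**What the plan says.** Section 12.4.2 says that the primary safety data given as percentages, namely ischemia/necrosis, erythema and dehiscence, "will be characterized in terms of distributional characteristics such as the maximum, mean, median, and variation (as 95% confidence interval". It does not name the interval method. Section 12.3 does, for primary and secondary outcomes alike: "Descriptive statistics will be employed including t distribution for continuous variables, Poisson distribution for incidence rates, etc. and 95% confidence intervals will be applied". Section 12.1 says the same.

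Section 10.2.3 has the surgeon score ischemia/necrosis and dehiscence for each graft from 0 to 100%. Erythema appears as a percentage only in 12.4.2; neither 10.2.3 nor the study calendar lists it as a score. No section gives a rule for truncation, transformation, resampling or an all-zero result.

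Section 10.2.2 defines the primary safety endpoints as presence or absence of each complication, necrosis and infection among them. In 12.4.2 necrosis and dehiscence are summarised only by extent, and infection is a percent with no interval mentioned there. Section 12.6.2 says that the sample is not meant for definitive conclusions, but that the trial will "provide support that the NAC graft is safe for marketing purposes".

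**The concern.** A t interval for a mean works when the sample mean is roughly normal and the sample SD is a fair guide to spread. Fifteen scores with a floor at 0, most of them perhaps exactly 0, can be far from that. The interval then fails in three ways: it has no width when nothing is seen, it includes impossible negative values when little is seen, and its upper end is too low because the rare large values are usually missing from the sample.

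For a safety measure the third failure does the most harm, because the error runs towards reassurance. A reported interval of 0% to 0% for necrosis could be read as showing that the risk has been excluded, in a trial whose data are meant to support marketing. The median and maximum do not help in that case, since both would also be 0.

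**Working it through.** The plan states no precision, expected event rate or power, so there is no figure of its own to reproduce. The planned interval was computed directly.

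**Inputs**
- Patients: 15 (Section 12.6.2). Scores are per graft, and Section 2.4 allows one or two grafts per patient without giving the split, so there are 15 to 30 grafts. The base case is 15 grafts, all unilateral.
- Scale: 0 to 100% (Section 10.2.3).
- Interval: mean ± t(0.975, n-1) × SD/√n (Sections 12.1 and 12.3). For n = 15, t = 2.145.
- Number and extent of affected grafts: not in the documents. Every value below is an assumption, shown over a range.

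**Step 1: none or one graft affected, n = 15**
- All zero: mean 0, SD 0, interval 0 to 0. This holds for any n.
- One graft at 30%: mean 30/15 = 2.0; SD = 30/√15 = 7.75; SE = 7.75/√15 = 2.0; 2.0 ± 2.145 × 2.0 = -2.3% to 6.3%.
- One graft at 100%: mean 6.7, SD 25.82, interval -7.6% to 21.0%.

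**Step 2: when the lower limit is negative**

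The condition is mean/SD < t/√n = 2.145/√15 = 0.554. With k grafts at one common extent and the rest at 0, mean/SD = √[k(n-1) / (n(n-k))], which does not depend on the extent.

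| k (n = 15) | mean/SD | Interval if extent is 20% |
|---|---|---|
| 1 | 0.258 | -1.53 to 4.19 |
| 2 | 0.379 | -1.23 to 6.56 |
| 3 | 0.483 | -0.59 to 8.59 |
| 4 | 0.583 | 0.26 to 10.40 |

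Unequal extents can keep the limit negative for longer: 5, 10, 20, 30 and 60% with ten zeros gives -1.0% to 17.7%. If every graft has some involvement (5 to 20% each, mean 12, SD 5.28), the interval is 9.1% to 14.9% and nothing is amiss. With 30 grafts at the same 20% extent, the lower limits for one to four affected are -0.70, -0.56, -0.28 and 0.08.

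**Step 3: the upper limit**

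A simulation of 100,000 trials per row assumed independent grafts, a share p affected, and extent among affected grafts of 100 × Beta(1,3), mean 25%. The true mean extent is therefore 25p. These are illustrative assumptions, not figures from the plan.

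| Grafts | p | Interval 0-0 | Lower limit < 0 | Coverage | Upper limit below true mean |
|---|---|---|---|---|---|
| 15 | 0.05 | 46.0% | 54.0% | 47.6% | 52.4% |
| 15 | 0.10 | 20.7% | 78.5% | 66.4% | 33.5% |
| 15 | 0.20 | 3.5% | 87.0% | 80.8% | 19.1% |
| 15 | 0.50 | 0.0% | 19.2% | 91.1% | 8.3% |
| 30 | 0.05 | 21.3% | 77.9% | 65.5% | 34.4% |
| 30 | 0.20 | 0.1% | 44.9% | 87.6% | 12.1% |

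Nearly all the missed coverage lies at the upper limit. Part of it is the 0-0 interval itself, but at p = 0.20 with 15 grafts only 3.5 of the 19.1 points come from that.

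**Step 4: incidence per patient**
- 0/15, exact (Clopper-Pearson): upper limit 1 - 0.025^(1/15) = 21.8%.
- 0/15, Poisson as named in the plan: upper limit -ln(0.025)/15 = 3.689/15 = 24.6%.
- 1/15: exact 0.2% to 31.9%; Poisson 0.2% to 37.1%.

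Mean extent and incidence are different quantities. The 21.8% is therefore not a corrected value of the 0% upper limit on mean extent; it answers the question that Section 10.2.2 asks.

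**The case against.** A reader might infer that all the primary safety intervals are wrong. The documents do not support that. Section 10.2.2 makes presence or absence the primary safety endpoint, and Sections 12.1 and 12.3 name Poisson for incidence rates, which gives a sensible 0 to 24.6% for 0/15. The t interval bears only on the extent scores, which are also reported by median and maximum.

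Nor is a negative limit certain. It depends on few grafts being affected, and no expected rate is documented. The t method has to be read into 12.4.2 from two general sentences that end in an open-ended abbreviation, which leaves the analyst some latitude. The study is descriptive, 12.6.2 disclaims definitive conclusions, and the criteria in 12.7 for going on to a larger study use no interval on mean necrosis or dehiscence.

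All of this stands and limits the point to reporting. It does not remove it. The t distribution is the only method the plan names for continuous data, the 0-0 collapse follows from it with certainty when all scores are zero, and 12.4.2 never applies the Poisson rule to necrosis or dehiscence. As written, the analysis section gives two complications no incidence summary and infection no stated interval.

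**Conclusion.** The point holds for the means of percent necrosis, erythema and dehiscence, and for those only. The 0-0 interval in an all-zero sample needs no assumption beyond the t rule in Sections 12.1 and 12.3. The negative lower limit and the low upper limit rest on the assumption that few grafts are affected; with equal extents the negative limit occurs for one to three affected grafts, both at 15 and at 30 grafts. In the illustration with 15 grafts, coverage of the nominal 95% interval was about 48% with 5% of grafts affected and 91% with half affected, so the fault fades as involvement becomes common. The simulation treats grafts as independent, which two grafts in one patient are not.

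This is a reporting flaw in a descriptive study that should be corrected. No figure in the plan is contradicted and no stated decision rule depends on the interval. It matters because the safety data are meant to support marketing and because the analysis in 12.4.2 does not match the endpoint in 10.2.2.

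**What to change.** In Section 12.4.2:

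- Report the number and percent of patients with any necrosis, any dehiscence and any infection at any visit, each with an exact (Clopper-Pearson) 95% CI. Say that any means a score above 0, and that infection means category C or D of Section 10.2.3, where B is labelled as no infection. Counting patients also avoids treating two grafts in one woman as independent.
- Describe the worst extent per graft over the visits by median and range, including the maximum, for necrosis, dehiscence and erythema. If erythema is to be kept, add its scale to Section 10.2.3.
- Drop the t interval on these percentages, and add to Sections 12.1 and 12.3 that the t rule does not apply to them.

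The cost is analysis wording only, with no added visits, patients or measurements. With no events, the report would show an incidence upper limit of about 22% in place of an uninformative 0-0 interval on mean extent. That limit is slightly below the 24.6% from the plan's own Poisson method, so the change does not make the incidence result look worse than the plan already allows.
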